4.2 Exclusion Criteria

Candidates meeting any of the following exclusion criteria at baseline will not be enrolled:

- Average LBP characterized as severe in the month preceding the current episode/aggravation
- Specific non-mechanical causes of LBP (e.g., infection, cancer)
- Contraindications to SMT or SSM (e.g., spinal fracture, progressive neurological deficits, inflammatory arthropathies of the lower back, surgical fusion of lumbar spine)
- Active management of current episode of LBP by another healthcare provider. Participants must stop management with their current provider to enroll in the study (e.g., SMT, PT, prescription medication, CBT, a structured program led by a healthcare provider that may include pain education, mind-body practices, coping strategies etc).
 - Participants taking prescription opioid medication for LBP are required to obtain a note from a prescribing/medical provider to confirm they have safely discontinued their opioid medication.
- Serious comorbid health condition that either requires medical attention (e.g., severe hypertension, inadequately managed serious mental health conditions, substance abuse), or has a risk for general health decline over the next year (e.g., Parkinson's disease, Multiple Sclerosis, organ failure, Dementia, Alzheimer's disease).
- Pregnancy, current or planned, and nursing mothers during the study period.
- Inability or unwillingness to give written informed consent.

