5. STUDY INTERVENTIONS

Patients will be randomized to one of the following treatment groups within the 2x2 factorial design: (1) SMT, (2) SSM, (3) the combination of SMT+SSM, or (4) MC. The initial treatment period is 8 weeks. Decisions regarding visit frequency will be made collaboratively by the provider and patient, as is typical in real-world settings. Participants will be required to attend 75% of prescribed intervention visits to be considered compliant over the 8-week period. In addition, participants have the option to receive additional treatment in the group to which they were randomized if they experience a recurrence of an acute LBP episode during the 10 month follow-up period. This additional treatment will occur in the same study clinic, or virtually using HIPAA compliant Zoom, with the same provider when possible. Participants will not be offered the option to receive treatment delivered in any of the other 3 study groups.

The primary goal of SMT is to address the biological and physical aspects of LBP (e.g., spinal dysfunction) with the intention of restoring maximum movement and functional ability of the spine. The goals of SSM are to primarily address the psychosocial aspects of acute and sub-acute LBP, by providing patients' the opportunities to develop their capacity and motivation to self-manage their LBP in an adaptive manner.^{45 108} The goals of the MC group will be to provide care for acute and subacute LBP as it would typically be delivered in primary care settings.

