5.3 Concomitant Interventions

Required Interventions

All participants will receive basic standardized information regarding the generally favorable prognosis of acute and sub-acute LBP. We will provide patients with an updated version of the Back in Action book ¹¹
⁴⁴ in print and/or electronic formats. The Back in Action book:

- Encourages patients to engage in their normal activities as soon as possible, even if it causes some pain.
- Encourages general aerobic exercise like walking, swimming, bicycling.
- Provides a very brief summary of the general causes of LBP, reassurance that it is rarely due to a serious problem, and that the majority of cases do not require specialty care or imaging.
- Emphasizes the patient's role in facilitating their own recovery by providing some general recommendations for symptom management (e.g., use of heat, changing positions frequently).

Allowed Interventions

Participants will be allowed to use OTC medications as needed during the course of the study. In addition, participants will be allowed to continue self-care practices (e.g., heat, stretching) for LBP they used prior to the study. Participants not assigned to MC who experience a significant worsening of LBP symptoms that cannot be managed by the assigned and concomitant interventions will be referred to the study's

medical care provider for a short-course of ‘rescue medications’, using a protocol successfully implemented, but rarely required, in previous studies by the investigators.^{10 11} See section 5.5.

Treating clinicians, in consultation with the PIs, may refer in the case of AEs or if LBP complications develop that cannot be adequately managed with the assigned intervention (e.g., disc herniation with progressive neurological deficits). Participants will be informed to seek any required care for all conditions unrelated to the study.

Prohibited Interventions

Participants will be asked to limit treatment to their assigned intervention for the length of the initial 8-week intervention period; similarly providers will be taught to refrain from delivering interventions that fall outside the scope of the study protocols (see above). However, participants retain the right to discontinue care at any time.

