- We have evaluated the impact on the power of our study subject to the potential for up to 240 subjects enrolled during restricted randomization. In our original protocol we focused sample size on obtaining adequate power for the Aim 1 chronicity endpoint assuming treatment relative risks of 0.70 (a 30% relative reduction), no interaction between treatments, and a control rate of 0.20. For this original scenario we used simulations to compute a power of 81% for either the overall SSM effect or the overall SMT effect. With partial randomization and an upper bound of n=240 subjects allocated during this period we obtain 78% power to detect an overall SSM effect and 77% power to detect an overall SMT effect. Therefore, the impact of altering the design to permit partial randomization is anticipated to have a minor reduction in power for our binary endpoints. In addition, the planned design will result in a minimum of n=30 per protocol pre-COVID subjects in the SMT and SSM+SMT groups combined with a full factorial randomization allocation of n=188 will permit a total of n=30+188=218 subject per group to evaluate mean differences in pain and disability scales across the four treatment groups. For MC and SSM groups we expect to have an upper bound of n=45 pre-COVID, n=120 partial randomization, and n=188 full factorial randomization subjects or n=45+120+188=354 total subjects per group. Our original balanced allocation would have produced n=1180/4= 295 subjects/group.

Statistical Analysis Plan

Introduction: A factorial trial is ideal when the two treatments under study are thought to act independently via different mechanisms.¹⁴⁶ Our interventions focus on a physical treatment approach (SMT) and a psychological intervention (SSM) for addressing acute LBP. A factorial design allows an efficient evaluation of each of these modalities using fewer subjects than would be required by separate trials. In addition, a crucial advantage of a factorial trial is the ability to evaluate whether the beneficial effects of each treatment modality combine in an additive, antagonistic, or synergistic fashion through evaluation of treatment interaction.¹⁴⁷

The trial was originally powered to detect meaningful differences in two dichotomous primary outcome measures, chronicity and recovery. These two outcomes are now secondary effectiveness measures.

Figure 9.1: The 2x2 factorial design (n=1000)

	SMT Intervention	No SMT Intervention

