SSM Intervention	SMT + SSM Group A	SSM only Group B
No SSM Intervention	SMT only Group C	Usual Medical Care Group D

For the 3 quantitative primary outcomes collected longitudinally, RMDQ, Pain NRS and LBP-Impact we will conduct detailed analysis of the four groups formed by the factorial design since we have excellent power for such endpoints with our revised sample size of 1000 subjects. However, McAlister et al.¹⁴⁶ comment that “the most powerful analysis of a factorial trial is performed at the margins” and we adopt such an approach for our secondary binary chronicity and recovery outcomes. We explicitly define the separate treatment effects for SMT and SSM as the overall or average treatment effect that is obtained from pooling comparisons over strata defined by the other treatment approach (i.e., the SMT treatment effect obtained by pooling over strata

with and without SSM). In particular, we define the parameter of interest as a linear combination (contrast) of parameters from an appropriate regression model that acknowledges the potential for SMT and SSM interaction. Therefore, our proposed analyses for binary outcomes do not make any additive assumptions and is quite generally valid for creating meaningful overall effect summaries. Furthermore, by collecting detailed outcomes and health care utilization through one year we can conduct thorough mediation analyses and careful evaluation of concomitant treatment.

Our statistical analysis plan focuses on the effectiveness evaluation detailed under the Primary Objective in the protocol. We also provide a plan for mixed methods analyses (qualitative/quantitative) associated with the Secondary Objective: implementation.

Primary Effectiveness Outcome # 1: prevention of cLBP that is impactful at 10-12 months follow-up (LBP Impact scale (min 8 - max 50) using mean from months 10-12). The LBP impact scale includes measures of pain intensity, pain interference, and physical function from the PROMIS-29 Profile v2.0) we will determine the effectiveness of SMT, SSM, and the combination of SMT+SSM relative to medical care (MC)

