Table 9.1: Chronicity based on LBP-Impact averaged over months 10-12 of follow-up. Power for the overall F-test of equality of means under various alternative scenarios. (alpha = 0.05)

Alternative	SMT Alone	SSM Alone	SMT + SSM	Power
Additive	0.20	0.20	0.40	93%
Sub-Additive 1	0.25	0.25	0.35	91%
Sub-Additive 2	0.30	0.30	0.30	94%
Sub-Additive 3	0.25	0.25	0.25	81%
Single effect 1a	0	0.30	0.30	98%
Single effect 1b	0.30	0	0.30	94%
Single effect 2a	0	0.25	0.25	91%
Single effect 2b	0.25	0	0.25	80%

In this model a test of $H_0: \beta_5=0$ allows us to determine if there is strong evidence for synergistic or antagonistic effects associated with combined treatment.

Secondary Effectiveness Outcome of Chronicity: Chronic back pain: For a subject to be classified as a chronic back pain patient at the 1-year assessment they must endorse having “a back pain problem that has persisted at least 3 months and has resulted in pain on at least half of the days in the past 6 months”. This outcome is based on specific items

from the NIH Research Task Force recommended minimal data set:⁷³ Question 1 on LBP duration; and Question 2 on the proportion of days that LBP has been a problem in the past 6 months. To evaluate chronic back pain we will consider the 1-year status as a key secondary outcome for chronicity prevention, and will use the 6-month status as another key secondary outcome.

Chronicity Hypothesis: SMT alone will decrease the rate of cLBP by 6-9% from a baseline MC level anticipated to be 20% or higher. Similarly, SSM alone will decrease the rate of cLBP by 6-9%, and the combination of SMT+SSM will lead to an additive net reduction.

Secondary Chronicity outcome Analysis: The analysis of the secondary binary outcome will use parallel marginalized tests of the average SMT treatment effect and the average SSM treatment

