likelihood ratio test of one treatment modality (either SMT or SSM). For simulations we considered crude analysis while our formal analysis will additionally adjust for site and baseline risk and therefore improve power since these are variables that only predict outcome and are not related to treatment group. For each scenario we simulated 5,000 data sets and empirically calculated power as the percentage of replicates in which the null hypothesis was rejected.

Using simulations with n=1000 subjects, 90% follow-up, and accounting for our imbalanced allocation due to COVID interruption we compute power for analyses that consider individual marginal treatment effects for both SMT and SSM. If we assume a UMC chronicity rate of 20% and a relative risk of 0.65 (rate under treatment = $20\% * 0.65 = 13\%$, or an absolute risk reduction of 7%) then we have >85% power to detect average SSM or SMT effects. If we a smaller effect corresponding to a relative risk of 0.70 (rate under treatment = $20\% * 0.70 = 13\%$, or an absolute risk reduction of 7%) then we have approximately 70% power to detect average SSM or SMT effects of this magnitude (specifically accounting for imbalance power is 72% for SSM and 70% for SMT). Power is greater for any relative risk when the UMC rate is increased to 30% or 40%. These relative risk effect sizes equate to medium effect sizes and are considered clinically important by Cochrane's Back Review Group.¹⁴⁸ We have not powered the study to detect interaction for the binary chronicity endpoint, but rather have powered the study to detect interaction on the underlying function and disability scales (see below).

Furthermore, we have excellent power to detect interaction effects where the effect of SMT and SSM may be synergistic or antagonistic, and using alpha=0.05 we have >80% to detect a X-point difference in LBP Impact treatment effects of one modality across the strata defined by the other treatment modality.

Secondary Effectiveness Outcome of Recovery: Determine the effectiveness of SMT, SSM, and the combination of SMT+SSM relative to medical care (UMC) in promoting recovery from acute or subacute LBP at 6 months.

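### Medical care is given only in the no-SMT/no-SSM cell, so the interaction coefficient includes medical care's own effect, and the averages tested for chronicity and recovery do not answer hypotheses worded against medical care

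*Combined protocol and SAP*

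**What the plan says.** Section 9 presents the trial as a 2x2 factorial. Its introduction lists as a crucial advantage the ability to learn "whether the beneficial effects of each treatment modality combine in an additive, antagonistic, or synergistic fashion through evaluation of treatment interaction". For LBP Impact, and again for pain and disability, it fits an interaction model with SMT, SSM and their product, and states that testing the product coefficient "allows us to determine if there is strong evidence for synergistic or antagonistic effects associated with combined treatment". The paragraph on factorial model assumptions, under potential problems, reads a synergistic result as the two therapies doing more together than separately, with implications for how they should be used.

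In Figure 9.1 the cell with neither intervention is "Usual Medical Care Group D". Sections 5.1.4 and 5.2.3 describe this as active care: visits with a medical provider, first-line anti-inflammatory drugs or muscle relaxants, and other drug classes where those fail or are not tolerated. The other arms are kept apart from it:

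- Section 4.2: "Participants must stop management with their current provider to enroll in the study".
- Section 5: "Participants will not be offered the option to receive treatment delivered in any of the other 3 study groups".
- Section 5.3: "Participants will be asked to limit treatment to their assigned intervention for the length of the initial 8-week intervention period".

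The exceptions are over-the-counter drugs in every arm (section 5.3) and a short course of rescue medication after significant worsening (section 5.5).

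For the secondary binary outcomes, the chronicity hypothesis is that "SMT alone will decrease the rate of cLBP by 6-9% from a baseline MC level anticipated to be 20% or higher", with parallel statements for SSM and the combination. The recovery objective is to "Determine the effectiveness of SMT, SSM, and the combination of SMT+SSM relative to medical care (UMC) in promoting recovery". The tests specified are of two averages from the logistic Full Model, β3 + ½β5 for SMT and β4 + ½β5 for SSM.

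**The concern.** A product term measures how two treatments combine only if the cell with neither treatment shares the background of the other three. Here that cell holds a third active treatment. If MC helps, the reference cell is better than the shared background, so both single-arm differences from MC shrink. The combination's difference from MC then looks larger than their sum, even when SMT and SSM simply add. The plan does not say that its synergy reading requires MC to have no effect of its own.

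The trial could therefore report synergy that is only MC's effect, or miss antagonism that is present. For chronicity and recovery the stake is narrower: the quantity tested is not the one the hypothesis and objective name.

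**Working it through.** Notation: β5 here always means the product coefficient of the interaction model or the logistic Full Model. In the Four Groups model the same symbol is the combination-versus-MC difference.

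**1. What β5 estimates.** Work on a benefit scale (higher is better; LBP Impact, pain and disability run the other way, so signs flip on the raw scales). Relative to the shared background of the book and over-the-counter drugs, let the cell means be MC = m, SMT = s, SSM = b, SMT+SSM = s + b + i, where i is the true SMT-by-SSM interaction. Then

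β5 = (s + b + i) − s − b + m = **i + m**.

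In the plan's Table 9.1, the Additive row (0.20, 0.20, 0.40) gives β5 = 0, so i = −m. The Sub-Additive 1 row (0.25, 0.25, 0.35) gives β5 = −0.15, so i = −0.25 if m = 0.1.

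**2. Standard error.** Section 9 expects about 300 each in MC and SSM and 200 each in SMT and SMT+SSM, with 90% followed: 270/270/180/180. In SD units,

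SE = √(2/180 + 2/270) = **0.136**.

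Period adjustment leaves this unchanged, because β5 = (SMT+SSM − SMT) − (SSM − MC) and each bracket can be compared within period.

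**3. The plan's own interaction power.** At alpha 0.05/2 (two-sided assumed, z = 2.241) the plan claims more than 80% power for 2.7 RMDQ or 1.3 pain points, with SDs of 6.5 and 3.0:

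- RMDQ: 2.7/6.5 = 0.415 SD; 0.415/0.136 − 2.241 = 0.81; power 79.1%.
- Pain: 1.3/3.0 = 0.433 SD; 0.433/0.136 − 2.241 = 0.94; power 82.7%.

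With all 1000 analysed these become 83.6% and 86.8%. The arithmetic essentially reproduces; the question is what the contrast means.

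**4. False synergy when i = 0.** Chance = 1 − Φ(z − m/0.136). The documents give no m; section 2.1 says only that the main drug classes have small effects on pain against placebo. The range 0 to 0.3 SD is an assumption.

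| Assumed m (SD) | alpha 0.05, z = 1.960 (LBP Impact) | alpha 0.025, z = 2.241 (pain, disability) |
|---|---|---|
| 0 | 2.5% | 1.25% |
| 0.1 | 11% | 6.6% |
| 0.2 | 31% | 22% |
| 0.3 | 60% | 48.5% |

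**5. Antagonism masked.** With i = −0.3 SD, β5 is −0.3, −0.2 or −0.1 for m of 0, 0.1 or 0.2. It is detected 60%, 31% or 11% of the time at alpha 0.05.

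**6. Binary averages.** The average SMT effect is half (SMT vs MC) plus half (SMT+SSM vs SSM), on the log-odds scale. Two illustrations:

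- MC 20%, other three arms 14%: SMT vs MC OR = (0.14/0.86)/(0.20/0.80) = 0.65; SMT added to SSM OR = 1; average OR = √0.65 = 0.81.
- MC, SMT and SSM 20%, both 12%: SMT vs MC OR = 1.00; SMT added to SSM OR = (0.12/0.88)/(0.20/0.80) = 0.545; average OR = √0.545 = 0.74. By simulation (4,000 replicates, no period adjustment) the average SMT test is significant in about 39% of trials, although SMT equals MC.

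Neither illustration uses m. They show only that the tested quantity and the hypothesised one can differ.

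**The case against.** The plan frames its effects relative to MC, and additivity in Table 9.1 is on that scale. Testing β5 = 0 is a valid test of whether the differences from MC add up. The shared background in the algebra is a condition that no arm receives on its own. An active comparator is a deliberate pragmatic choice. The plan expects sub-additivity, and if m is zero or more a negative β5 still indicates antagonism, so the expected finding would be understated, not false. The relevant m is MC's increment over over-the-counter and rescue drugs. Treatment is confined to the assigned arm for only 8 weeks, while outcomes are averaged over 12 months or months 10–12. An m of 0.3 SD would equal the whole effect hypothesised for SMT or SSM over MC.

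All of this stands, and it limits the size of the problem. It does not rescue the wording: section 9 draws conclusions about synergy between SMT and SSM, not about additivity of differences from MC, and never states that this needs m = 0.

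On the binary outcomes, the average formulas are given openly, and the factorial-assumptions paragraph says that an average effect is what will be estimated under interaction. The same divergence arises in any factorial trial. That paragraph also quotes power for each arm against MC, and the Full Model already contains those contrasts. What remains is that no test or report of them is specified, although the hypothesis and objective are worded that way.

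**Conclusion.** The point holds as an error of interpretation in the interaction analyses and a mismatch between hypothesis and test for chronicity and recovery. β5 equals i + m, so it isolates the SMT-by-SSM interaction only if MC adds nothing to the shared background. Over an assumed m of 0.1 to 0.3 SD, the chance of falsely declaring synergy is 11% to 60% at alpha 0.05 and 6.6% to 48.5% at alpha 0.025. These figures rest on m, which the documents do not supply and which over-the-counter and rescue use would shrink.

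Four stronger readings are tempting but not supported:

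- A reader might infer that the interaction test is worthless. It validly tests additivity of differences from MC, and a negative β5 still shows antagonism if m is zero or more.
- A reader might infer that the main results are compromised. The 3-df tests for LBP Impact, pain and disability, and their arm-versus-MC contrasts, do not depend on m.
- A reader might take the binary examples as proof of distortion by MC, or of reversed direction. They are ordinary divergence between average and simple effects, and neither reverses direction.
- A reader might infer that arm-versus-MC results for the binary outcomes are unavailable. They are in the Full Model but not named as results.

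**What to change.** 1. **Interaction.** Where section 9 interprets β5 (LBP Impact; pain and disability; factorial model assumptions), describe it as departure from additivity of the differences from MC, which includes MC's own effect. Do not read a positive β5 (benefit scale) as synergy. Report SMT+SSM versus SMT (β4 + β5) and SMT+SSM versus SSM (β3 + β5) as the evidence on the value of combining. These estimands are free of MC.

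2. **Chronicity and recovery.** From the Full Model, report β3, β4 and β3 + β4 + β5 as the SMT, SSM and combination results against MC. Keep the averages, labelled as half versus MC and half added to the other intervention.

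3. **Optional.** Show β5 − m over a range of assumed m. Do not attach a fixed decision rule: requiring synergy to survive m = 0.3 would need an estimate of about 0.3 + 1.96 × 0.136 = 0.57 SD and would rest on an unsourced bound.

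Cost: SAP wording and extra contrasts from models already planned, with no new data or sample size. The interaction claim becomes weaker and the binary arm-versus-MC intervals are wider. With 20% under MC, 13% under each single intervention and additive risks, simulated power (4,000 replicates, no period adjustment) is about 49% for SMT and 60% for SSM against MC, compared with 88% and 87% for the averages.
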